# Section G: Sample Size/Data Analysis

#### G1. Sample Size

How many subjects (or specimens, or charts) will be used in this study? Local: 50 Worldwide: 50

Please indicate why you chose the sample size proposed:

There is no prior studies to report the major primary outcomes for comparison between DermaCELL and Integra. Based on interviewing our podiatrist who worked with both Integra and DermaCELL, we estimated the time needed to apply each matrices in the OR. We hypothesized that time needed to apply DermallCELL is approximately 3±2 min while the time needed to apply Integra is estimated to be 5±2min (Cohen¿s effect size d=1). Assuming an alpha of 5% and power of 80% and two tailed t-test comparison, 17 subjects per group needed to be recruited to observe a significant difference between two groups from point of view of application time. We anticipate that this sample size should be also sufficient to observe noticeable trend in other outcomes. Based on results of this study, another RCT may be addressed to clinically validate the

observed noticeable trends. Alternatively, the sample size may be increased upon available of budget, approval of sponsor, and noticeable observed trend based on the first 20 recruited subjects (ten per group).

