# Section F: Design/Procedure

## F1. Design

Select one category that most adequately describes your research:

c) Pilot

Discuss the research design including but not limited to such issues as: probability of group assignment, potential for subject to be randomized to placebo group, use of control subjects, etc.

Thirty four (n=50) patients with diabetes (age 18 years or older) with non-infected deep wounds (grades 2 in the Wagner Ulcer classification) will be randomized into two groups, 17 subjects per group each. The group one will be treated by Meshed DermaCELL and group two will be treated by Meshed Integra template.

The primary outcomes are time to granulation, successful granulation at 8 weeks, and number of failures (e.g. amputation, infection, rejection, re-application) within 8 weeks. Secondary outcomes include time to apply, weekly speed of wound healing after successful granulation and transition to standard wound therapy, success of wound healing at 12 weeks and @16 weeks, cost of wound treatment upto 16weeks (based on patient electronic record), tissue biomechanics after wound healing (e.g. presence of scarring or tissue biomechanics properties leading to increase in shear or pressure post healing), change in skin perfusion (assessed with SPP), change in thermography response, recurrence of ulcers up to 6 months post healing, and other patient centered outcomes including perception of pain, physiological stress response as surrogate of pain (e.g. heart rate variability during dressing change), sleep quality (assessed by PSQI and sensor-based sleep quality index), wound smelling (assessed by Likert scale), and patient perception of benefit (assessed by technology acceptance model, TAM based on perception of benefit and attribute of benefits).

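### G1 sizes the trial on application time, a secondary outcome, and says without support that the same size will do for the other outcomes, which include all three primary outcomes

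*Combined protocol and SAP*

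**What the plan says.** G1 contains one calculation. It assumes that "time needed to apply DermallCELL is approximately 3±2 min while the time needed to apply Integra is estimated to be 5±2min", a standardised difference of 1. "Assuming an alpha of 5% and power of 80% and two tailed t-test comparison", it concludes that "17 subjects per group needed to be recruited to observe a significant difference between two groups from point of view of application time". F1 places this outcome among the secondary ones: "Secondary outcomes include time to apply, weekly speed of wound healing after successful granulation".

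F1 and G2 name three primary outcomes: time to granulation, successful granulation at 8 weeks, and number of failures within 8 weeks. G1 acknowledges that no earlier study reports these for the two products. It gives no rate, hazard or failure count for them, and then says: "We anticipate that this sample size should be also sufficient to observe noticeable trend in other outcomes". The term for the trend is not defined.

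G1 attaches two possible decisions to such a trend. One is a further trial: "Based on results of this study, another RCT may be addressed to clinically validate the" trends seen here. The other is a larger sample, subject to budget and sponsor approval, if a trend shows in the first 20 patients.

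Three other statements bear on the point. F1 classes the study as a pilot. G2 plans all p-values at a two-sided 0.05. The size itself is stated in two ways: F1 says patients "will be randomized into two groups, 17 subjects per group each", while G1 lists "Local: 50 Worldwide: 50".

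**The concern.** A standardised difference of 1 in minutes of application time says nothing about a proportion, a hazard or a count. The sentence in G1 nevertheless carries the sizing over to the outcomes the trial calls primary, and it is the only justification of size the plan offers for them. A sponsor or reader could take it as assurance that the primary comparisons will be informative. Because a follow-on trial or a larger sample may rest on an observed trend, it matters how wide the estimates will be and how often a sizeable gap arises by chance.

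**Working it through.** **Inputs from the plan.** Means 3 and 5 min, SD 2, two-sided alpha 0.05, power 80%, t-test, 17 per group (G1); 50 patients in total (G1), which at equal allocation is 25 per group.

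**Assumed, because the plan gives no figure.** Granulation at 8 weeks 50-70%; 20 to 34 granulation events at 17 per group (30 to 50 at 25 per group) with proportional hazards; 0.2 to 0.8 failures per patient in the lower-rate group, Poisson; no dropout.

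**1. The plan's own figure.** d = (5 − 3)/2 = 1. The normal approximation gives 2 × (1.96 + 0.8416)²/1² = 15.7, so 16. The noncentral t gives 16.7, so 17. At 17 per group (32 df, noncentrality √(17/2) = 2.92) power is 80.7%; at 25 per group it is 93.4%. The stated 17 reproduces.

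**2. Precision for granulation at 8 weeks.** Half-width of the 95% CI for the difference = 1.96 × √(2p(1 − p)/n).
- n = 17: 1.96 × √(0.50/17) = 33.6 points at p = 0.5; 1.96 × √(0.42/17) = 30.8 points at p = 0.7.
- n = 25: 27.7 and 25.4 points.

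**3. Gaps that arise with no true difference.** Exact binomial enumeration, both groups at the same p. At 17 per group, 15 points means a gap of at least 3 patients (3/17 = 17.6 points) and 20 points at least 4 (4/17 = 23.5 points).

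| Per group | Gap | p = 0.5 | p = 0.6 | p = 0.7 |
|---|---|---|---|---|
| 17 | ≥15 points | 39.2% | 38.1% | 34.8% |
| 17 | ≥20 points | 22.9% | 22.0% | 18.9% |
| 17 | ≥25 points | 12.1% | 11.4% | 9.0% |
| 25 | ≥15 points | 32.2% | 31.2% | 27.9% |
| 25 | ≥20 points | 20.3% | 19.3% | 16.4% |

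At the look after 20 patients (10 per group), a gap of 20 points or more arises in 46-50% of trials over the same rates.

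**4. Differences that 17 per group could detect with 80% power.**
- Granulation: about 50% v 92%. Exact power there is 81% with the uncorrected chi-square and 70% with Fisher's test. From a base of 70%, no improvement reaches 80% power.
- Time to granulation, HR = exp(2 × 2.8016/√events): 34 events, exp(0.961) = 2.6; 20 events, exp(1.253) = 3.5.
- Failures, solving ln(RR) = 2.8016 × √(1/(nr) + 1/(nr·RR)): at r = 0.8, nr = 13.6 and RR = 2.5; at r = 0.2, nr = 3.4 and RR = 5.2.

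**5. Precision for the other two primary outcomes with no true difference.** The 95% CI multiplies and divides the estimate by a factor.
- HR, exp(1.96 × 2/√events): 1.96 (34 events) to 2.40 (20 events) at 17 per group; 1.74 (50) to 2.05 (30) at 25 per group.
- Failure rate ratio, exp(1.96 × √(2/(nr))): 2.1 (r = 0.8) to 4.5 (r = 0.2) at 17 per group; 1.9 to 3.5 at 25 per group.

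**The case against.** The strongest reply is that G1 promises little. It says only that the authors anticipate seeing a trend, immediately after tying the 17 to application time. It states no power for any primary outcome. The study is classed as a pilot, and a later trial is mentioned as the place to validate what is seen. All of that stands. A reader might infer from the detectable differences above that the plan claims power it lacks, or that its arithmetic is wrong. The documents support neither: the one stated figure reproduces, and low power contradicts nothing that is written.

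A reader might also infer that any observed trend would be largely noise. That goes too far. The frequency of chance gaps depends on the cutoff, and the plan sets none: at 17 per group it falls from 35-39% at 15 points to 9-12% at 25 points, and at a granulation rate of 80% the 15- and 20-point figures are 28% and 13%. If the true rates were 60% v 75%, the observed direction would be right in 78% of trials, tied in 9% and reversed in 13%.

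What the reply does not rescue is the word sufficient. The plan offers no basis for it, calls these outcomes primary, tests them at 0.05, and may act on what it sees. Section D also assumes that wound outcomes are comparable between the products, so the no-difference case is close to the plan's own expectation.

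**Conclusion.** The point holds as an unsupported statement of adequacy, not as an arithmetic error. The trial is sized for a secondary outcome, and nothing shows that this size is adequate for the three primary ones. At 17 per group the granulation difference would be known only to within about ±31 to 34 points, and a chance gap of 15 points or more would appear in over a third of trials. Conventional power would need very large effects: about 50% v 92% on granulation, an HR of about 2.6-3.5, or a failure rate ratio of about 2.5-5.2. At 25 per group the picture is milder but the conclusion is unchanged: ±25 to 28 points, with chance gaps of 15 points or more in 28-32% and of 20 points or more in 16-20%.

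These sizes rest on the assumed rates, event counts and Poisson failures. Dropout or overdispersed counts would widen the intervals. Severity: should-fix.

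**What to change.** 1. Reconcile 34 and 50 patients across F1 and G1, so that the figures below refer to one size.
2. Replace the sentence in G1 with: *The sample size is set for application time only. It is not sized for the primary outcomes, which will be reported as estimates with 95% CIs and treated as exploratory.* Follow it with the expected precision at the actual size for all three primary outcomes, naming the assumed rates and the test or interval method. The test should be named because chi-square and Fisher differ by about 11 percentage points of power at 50% v 92%.
3. In G2, describe p-values for the primary outcomes as exploratory.
4. Revise the later references in G1 to observed trends, both for a further trial and for enlarging the sample after 20 patients, so that they agree with the new wording.

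I would not add a rule that bars a follow-on trial unless a difference is significant. With true rates of 60% v 75%, chi-square power at 17 per group is about 15%, so such a rule would block the next trial about 85% of the time, which defeats the purpose of a pilot.

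The cost is wording in G1 and G2, plus the reconciliation with F1. The stated adequacy becomes less favourable. No extra patients are needed.

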## A5. Funding Source:

Organization: LIFENET HEALTH

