# Section C: Background Information

Diabetes-related foot ulcers (DFUs) are a leading cause of hospitalization and amputation worldwide, and account for 33% of all direct costs of diabetes care in the US. Ulcers requiring acute care can result in treatment costs of up to US\$70,000 per event, varying with the severity of the wound. Once the skin is ulcerated, it is susceptible to becoming infected and ultimately amputation in particular in case of deep DFUs. To manage the cost and avoid hospitalization and amputation, wound should be immediately closed. But this is often challenging in diabetic foot with deep ulcers. Wound healing is a dynamic process involving interactions between cells, extracellular matrix (ECM) and growth factors that reconstitutes tissue following injury. ECM plays an important role in tissue regeneration and is the major component of the dermal skin layer. Recognition of the importance of the ECM in wound healing has led to the development of wound products that aim to stimulate or replace the ECM in particular in case of deep tissue destruction because of deep DFUs. It is known from the literature that chronic or hard-to-heal wounds are characterized by a disrupted or damaged ECM that cannot support wound healing. Thus treatment strategies based on use of biologic scaffold materials for management of chronic and deep wounds has increased dramatically during the past two decades. These scaffolds include those comprising an intact extracellular matrix (ECM) or individual components of the ECM, and those comprising hybrids incorporating a synthetic component with a biologic component. DermACELL (LifeNet Health, Virginia Beach, VA) is acellular dermal matrices (ADM), which has been shown to be effective in treating chronic DFUs in a clinical trial.

Another ADM product available in the market is made by Integra® (Bilayer Matrix Wound Dressing, Integra LifeSciences). However, advantages/disadvantages of one compared to the other are unclear. Figure 2 (Please see protocol in section S)illustrates the case showed in the figure 1 treated by both Integra and DermaCell (One of the wound was treated by Integra and the rest were treated by DermaCell). As it can be seen the thickness of Integra is higher than DermalCELL,

\*\*\*Please note that this is a reliance protocol\*\*\*

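### The sample size may rise on an undefined trend in the first 20 subjects while the final test stays at 0.05, so the type I error is not fixed: about 4.1% to 5.9% for N from 34 to 50

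*Combined protocol and SAP*

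**What the plan says.** Section G1 bases the size on application time: "time needed to apply DermallCELL is approximately 3±2 min" against "the time needed to apply Integra is estimated to be 5±2min", and "Assuming an alpha of 5% and power of 80% and two tailed t-test comparison, 17 subjects per group needed to be recruited". As an alternative to running a further trial, it allows the sample to be enlarged on three conditions: available budget, approval of the sponsor, and a "noticeable observed trend based on the first 20 recruited subjects (ten per group". It does not name the outcome to be examined, what counts as noticeable, who looks, or how large the trial may become.

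The planned total is itself unclear. F1 opens with "Thirty four (n=50) patients with diabetes" and continues that they "will be randomized into two groups, 17 subjects per group each". G1 lists 50 subjects. Neither section calls 50 the ceiling for the increase.

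G2 sets a two-sided 0.05 level for all p-values and makes no allowance for the look or the increase. H2 describes no monitoring arrangements, and no masking or independent review is described anywhere. A5 gives the funder as "Organization: LIFENET HEALTH". Section C identifies the same company with one of the two products: "DermACELL (LifeNet Health, Virginia Beach, VA) is acellular dermal matrices (ADM". F1 classifies the study as a pilot.

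**The concern.** A trend between groups can be seen only in data split by arm, so this is in substance an unmasked interim look. That is an inference, since the plan does not use the term, but it is hard to read ten per group in any other way. When the final N depends on the interim difference and the final test ignores this, the nominal 5% is no longer guaranteed. Depending on the rule, the true rate may be above or below 5%. With no written rule, nobody can say which applies, either beforehand or when the results are read.

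The decision also needs the approval of a sponsor that, if it is the funding organisation named in A5, makes one of the products. An undefined criterion leaves that decision open to influence by the direction of the early results.

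**Working it through.** **Inputs.** From G1: difference 2 min (5 − 3), SD 2, so d = 1; two-sided alpha 0.05; power 0.80; look at 20 subjects. From F1: 17 per group, so 34 in total. From G2: final level 0.05. Assumption: 50, as listed in G1, is the largest N.

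**The plan's own figure.** The normal approximation gives n = 2(1.960 + 0.842)²/1² = 15.7, so 16 per group. The exact t-test power is 0.781 at 16 and 0.807 at 17. The plan's 17 per group is reproduced.

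**Error rate with the look.** Let z1 be the statistic at 20 subjects and z2 that of the later N − 20. The plain final statistic is Z = (√20·z1 + √(N−20)·z2)/√N. Under the null, the chance of rejection given z1 is

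CE(z1, N) = 1 − Φ[(1.96√N − √20·z1)/√(N−20)] + Φ[(−1.96√N − √20·z1)/√(N−20)].

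The type I error is CE averaged over a standard normal z1, with N set by the rule.

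Example at z1 = 1:
- N = 34: (1.96×5.831 − 4.472)/3.742 = 1.859, so CE = 3.2%.
- N = 50: (1.96×7.071 − 4.472)/5.477 = 1.714, so CE = 4.4% with the small lower tail.

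Extending at z1 = 1 therefore raises the chance of a false positive. At z1 = 1.96 it lowers it, from 23.8% to 17.6%. The crossover is at |z1| of about 1.38.

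| Rule (34, or 50 if triggered) | Type I error |
|---|---|
| Fixed N = 34 | 5.0% |
| Increase if \|z1\| > 0.5 | 4.6% |
| Increase if \|z1\| > 1 | 4.2% |
| Increase if \|z1\| > 1.28 | 4.1% |
| Increase if \|z1\| > 1.96 | 4.4% |
| One direction only: z1 > 0, > 0.5, > 1 | 5.0%, 4.8%, 4.6% |
| Increase only if \|z1\| is 0.5 to 1.6 | 5.5% |
| Increase if \|z1\| < 1.28 | 5.9% |
| Worst-case choice of N from 34 to 50 | 5.9% |

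If 50 is not the maximum, the worst case rises to 6.4% for N up to 68 and 6.9% for N up to 100.

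**Check of the remedies.** Take the rule of extending to 50 when |z1| < 1.38. The plain test gives 5.9%. The inverse-normal statistic √(20/34)·z1 + √(14/34)·z2 gives 5.0%. Alternatively, a critical value of 2.030 (two-sided level 0.042) holds the worst case for N from 34 to 50 at 5%.

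**The case against.** The strongest reply is that the natural reading of G1 does not inflate the error. A larger trend means extend, and every simple threshold in the table gives 4.1% to 5.0%. Going above 5% needs something G1 does not state, such as an upper cutoff, extension on weak trends, or selective approval. This stands as to the expected effect. It does not show that 5% is held, because nothing in the text rules those variants out.

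The pilot label and the possible later trial also carry weight. They limit the consequence but do not remove it: G2 still plans tests at 0.05 for the primary outcomes, and G1 offers the extension as an alternative to that later trial. Testing three primary outcomes each at 0.05 is a separate matter.

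A reader might infer more than the documents support:
- **Unlimited growth.** This would give a worst case of 7.9%, but G1 lists 50 subjects, so open-ended enrolment is not what is described.
- **Repeated significance tests.** Testing at 34 and again at 50 would give 7.6%, and at 20, 34 and 50, 10.3%. No section plans such tests.
- **The funder or recruiters see the interim results by arm.** G1 requires only sponsor approval. Section K counts the sponsor among those with access to research data, but no section says who performs or sees the look. The accurate statement is that access is not excluded.
- **The 34/50 conflict shows that the option has already been used.** Nothing in the text says so.

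**Conclusion.** The concern holds in a limited form. The stated 5% is not guaranteed because the extension rule is undefined and the final test takes no account of it. Any inflation is possible rather than expected, and it is small: at most 0.9 percentage points (5.9% − 5.0%) if N cannot exceed 50, and simple trend-triggered rules are slightly conservative.

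These figures assume one outcome, the same outcome at the look and at the end, a normal test statistic, a base of 34, and no declaration of significance at 20. If 50 is the base rather than the ceiling, the worst case is 5.5% for N up to 68 and 6.0% for N up to 100. The more practical weakness is an undefined decision that needs sponsor approval, in a trial with no described masking or restriction on interim results.

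**What to change.** Preferred: delete the trend trigger from G1, fix the sample size, and state in F1 and G1 alike whether 34 or 50 is the planned number.

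If the look is kept:
- Name the outcome, the threshold, the decision maker and the maximum N before the first interim data are seen.
- Test the final result by an inverse-normal combination with squared weights fixed at 20/34 and 14/34, or use a final two-sided level of about 0.042 for a maximum of 50. Both figures assume a base of 34 and must be reset if the base or maximum differs (a maximum of 68 needs about 0.039, and 100 about 0.036).
- Keep by-arm interim results from the sponsor and recruiting staff, and say who holds them.

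The cost is protocol and analysis-plan wording. The downside is losing the informal option to extend or, if the look is kept, a slightly stricter or less familiar final test.

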## G2. Data Analysis

Provide a description of your plan for data analysis. State the types of comparisons you plan (e.g. comparison of means, comparison of proportions, regressions, analysis of variance). Which is the PRIMARY comparison/analysis? How will the analyses proposed relate to the primary purposes of your study?

The primary outcomes are time to granulation, successful granulation at 8 weeks, and number of failures (e.g. amputation, infection, rejection, re-application) within 8 weeks. Mixed models accommodate the longitudinal design; allow for testing differences between groups in patterns over time as well as at specific time points; are consistent with an intention to treat analysis (9), and are valid for data which are missing completely at random or at random (10). Number of failures as well as number of recurrence of ulcers over the 6 month follow-up will be modelled with a generalized linear model using an appropriate count outcome (Poisson, zero-inflated Poisson, negative binomial for overdispersion). Rate ratios comparing intervention arms will be estimated from this model. Appropriate mixed models (linear or generalized linear, for noncontinuous outcomes or logistic regression for binary data) will be used to test the intervention effect for each of the secondary outcomes (e.g. tissue biomechanics, mobility, patient centered outcomes, recurrence of ulcers, etc). A Kaplan-Meier survivorship analysis will be used for estimating time to event for none successful healing probability over time by treatment and the p-value will be calculated using the Log-rank (Mantel-Cox) test. Hazard ratios will be used to indicate the probability of closure at any given point in time for Derma-Cell v. Integra treatment. Univariate logistic regression analyses will be performed to delineate predictive factors of successful granulation at 8 weeks, successful wound healing at 12 weeks, and successful wound healing at 16 weeks. Results will be controlled for potential confounding variables including age, sex, BMI, HbA1c, neuropathy severity, vascular status, frailty, mobility status, and initial wound size. The p-values for weekly % wound area and % wound area reduction through 16 weeks will be calculated using t tests. All p-values, for both the categorical and continuous data, will be calculated using a two-sided alpha of 0.05.

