#### F2. Procedure

\*\* Reliance protocol \*\* There are a total of 17 study visits.

Medical History: The presence of diabetes will be determined based on American Diabetes Association criteria. This will include: duration and type of diabetes, type of diabetes medication (insulin, oral, combination therapy, diet), previous history of foot ulcers, amputation (toe, foot), lower extremity bypass, lower extremity angioplasty, Coronary artery bypass surgery, cardiac angioplasty, arthritis, liver disease, osteoporosis, malignancy, and bone tumors. We will use the Kaplan co-morbidity index to record disease severity.

Social and Economic Factors: We will evaluate the following factors: marital status, years of education, type of work, tobacco history (pack years, current smoker, current use of chewing tobacco, previous smoker, no tobacco history), drug history (current, previous history, no drug history), and alcohol history. Also we will collect cost information for the subject's treatment up to 6 months after the subject enrolls in the study.

Questionnaires: Quality of Life, Frailty Status, Sleep Quality, Cognitive Status and Device Acceptability: To evaluate functional status we will use well-accepted questionnaires, SF-12 for Quality of Life, Sleep Quality questionnaire (PSQI), MOCA and TSFI for frailty status. In addition, at each visit, we will interview the subject about their concern with their wound and product (e.g. wound drainage, smell, pain, etc.), use of any medications for pain or sleeping, the cost of transport to the clinic, any adverse events (e.g. infection, need to visit a specialist, etc), etc. To see the timeline for each questionnaire, please refer the table included in the ICF attached.

Pain Intensity Assessment (VAS): Researchers will provide a numerical pain scale where subject will report their pain intensity. Researchers will document pain level.

Adverse Event Reporting: Researchers will document and report any study/non study related incident as per institution regulations.

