Visit 16, Sixteen Weeks Later \*duration 90 min This visit will take place at Baylor Clinic for a regular follow up appointment. The researchers will perform as described above: Pain Questionnaire, Sleep Quality Questionnaire, Device Acceptability Questionnaire, Adverse Event Reporting, Dressing Change, Wound Photo, Thermal Image, Wound Assessment, Vascular Assessment, Granulation Assessment, Wound Care, Wifi Wound Classification, Upper Extremity Assessment.

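### Ulcer recurrence is defined to 6 months after healing, but the described visits stop at week 16 and the recurrence rate ratio has no stated at-risk set or time at risk

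*Combined protocol and SAP*

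**What the plan says.** All references are to the combined protocol and SAP.

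- **Outcome window.** F1. Design lists, among the secondary outcomes, "recurrence of ulcers up to 6 months post healing". The clock starts at healing.
- **Analysis.** G2. Data Analysis states: "Number of failures as well as number of recurrence of ulcers over the 6 month follow-up will be modelled with a generalized linear model". It does not say when the 6 months begin. It offers Poisson, zero-inflated Poisson or negative binomial models and promises rate ratios between arms. Later in the same section, recurrence also appears among the secondary outcomes to be tested with mixed models.
- **Follow-up.** F2. Procedure says "There are a total of 17 study visits". The visits described are baseline plus weeks 1 to 16, and the last is headed "Visit 16, Sixteen Weeks Later".
- **Later data.** The one collection described beyond week 16 is cost information, in F2 under Social and Economic Factors, for "treatment up to 6 months after the subject enrolls in the study". F1 gives cost a 16-week window, from the electronic record.
- **Attachments.** Section C refers the reader to another file ("Please see protocol in section S"). F2 says of the questionnaire timeline, "please refer the table included in the ICF attached". Neither was in the text available.

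**The concern.** There are two linked gaps.

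The first is capture. Healing is assessed at weeks 12 and 16, so some wounds may close late in the visit schedule. For those wounds the described visits see little or none of the 6 months after healing. F1 starts its clock at healing, the cost collection starts at enrolment, and G2 gives no start.

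The second is the denominator. A wound that never closed cannot recur, and one that closed late has had less time to recur. A rate ratio needs either time at risk or equal follow-up, and G2 states neither. It also does not say what happens to never-healed wounds. If they entered as zeros without an exposure term, the product that heals fewer wounds, or heals them later, would look better on recurrence.

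What is at stake is a descriptive trend. G1 expects this sample to show noticeable trends in other outcomes and says a further RCT may follow them up. A trend produced by who healed, and when, could misdirect that step.

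**Working it through.** **1. Visit count.** Baseline plus 16 weekly visits = 17. Section L agrees: $1275 / $75 per visit = 17. No paid visit is left over for follow-up after week 16.

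**2. Share of the window covered.** Take 6 months as 26 weeks and let h be the healing week. Coverage by visits is (16 − h)/26. Coverage by data to 6 months from enrolment is (26 − h)/26. The full window ends at week h + 26.

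| Healed at week | Visits to week 16 | Data to 6 months from enrolment | Full window ends |
|---|---|---|---|
| 8 | 8/26 = 31% | 18/26 = 69% | week 34 |
| 12 | 4/26 = 15% | 14/26 = 54% | week 38 |
| 16 | 0/26 = 0% | 10/26 = 38% | week 42 |

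**3. Effect of the missing denominator.** The documents give no healing times or recurrence rate, so these are assumptions. Suppose the recurrence hazard is equal in both arms, healing is exponential with median m, never-healed wounds count as zeros and there is no exposure term. Expected recurrences are then proportional to mean weeks at risk per randomised patient.

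With λ = ln 2/m, the proportion healed by week 16 is p = 1 − 2^(−16/m). Mean weeks at risk with data to week 16 are 16 − p/λ.

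- m = 8: λ = 0.08664, p = 0.750, mean = 16 − 8.66 = 7.34 weeks
- m = 12: λ = 0.05776, p = 0.603, mean = 16 − 10.44 = 5.56 weeks
- Ratio, faster-healing arm over slower: 7.34/5.56 = **1.32**. This is 1.24 from the proportion healed times 1.06 from time at risk among the healed.
- Equal medians: 1.00.

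With weeks at risk among healed wounds as the denominator, the expected rate ratio is 1.00 whatever the healing times.

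**4. Does longer follow-up help?** That depends on whether healing after week 16 is also recorded. The table gives the same ratio for medians of 8 and 12 weeks. The delayed pattern is Weibull with shape 3, for which p = 1 − 2^(−(16/m)^3).

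| Data available | Healing counted to | Exponential | Delayed |
|---|---|---|---|
| To week 16 | week 16 | 1.32 | 1.81 |
| To week 26 | week 16 | 1.28 | 1.44 |
| To week 26 | week 26 | 1.25 | 1.29 |
| 26 weeks after healing | week 16 | 1.24 | 1.23 |
| 26 weeks after healing | week 26 | 1.15 | 1.00 |

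In the last two rows the ratio is simply the ratio of proportions healed. For exponential healing counted to week 26 it is (1 − 2^(−26/8))/(1 − 2^(−26/12)) = 0.895/0.777 = 1.15.

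**5. Expected events.** Assume a 20% recurrence risk over 26 weeks, so a hazard of −ln(0.8)/26 = 0.0086 per week, with exponential medians of 8 and 12 weeks and data to week 16. F1 gives "17 subjects per group each" and G1 gives 50 in total, or 25 per arm if split equally. Expected patients with a recurrence are 1.02 v 0.77 at 17 per arm and 1.50 v 1.14 at 25 per arm. At 17 per arm, at least one arm has none in 64.5% of trials. The faster-healing arm shows more recurrences in 40.6%, the same number in 32.7% and fewer in 26.7%.

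**The case against.** **Capture may exist elsewhere.** A reader might infer that recurrence will not be recorded after week 16. The documents do not support that. The attached protocol and the consent-form table were not seen, and G2's wording presupposes a 6-month follow-up. Patients come mainly from the investigators' own practices, and cost uses the electronic record, so treatment records to week 26 could show a treated recurrence. This stands as a limit: the claim is only that the available text describes no such capture. The cost collection does not close the gap, since it is described for cost alone and runs from enrolment.

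**The bias depends on an analysis the plan does not state.** A reader might infer that G2 will enter never-healed wounds as zeros. It does not say so. F1's post-healing definition points to healed wounds, a rate ratio suggests person-time, and the zero-inflated option is a model that allows for structural zeros. That is fair. But none of these is stated as the rule, and a zero-inflated model would not by itself correct unequal time at risk.

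**Longer follow-up might be thought useless.** That holds only if healing after week 16 is ignored. When later healing is recorded, the bias shrinks and can vanish (step 4).

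**The effect is small and may be absent.** Section D assumes comparable healing, and then the ratio is 1.00. With about one expected recurrence per arm, chance dominates. This stands, and it limits the point to a descriptive trend. However, comparable healing is part of what the trial compares, so the recurrence analysis should not depend on it.

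**Conclusion.** The point holds for the text available. The described visits do not deliver the recurrence window in F1, and data to 6 months from enrolment would deliver only part of it. This rests on date arithmetic and on taking 6 months as 26 weeks. G2 also leaves the clock start, at-risk set, time at risk and choice between count and mixed model unstated.

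The ratio of 1.32 is an illustration, not a prediction. It requires never-healed wounds entered as zeros without an exposure term, healing that differs between arms, the assumed medians and exponential shape, and a week-16 limit on both data and healing.

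The point should be corrected, but it does not threaten the trial's main comparison. Recurrence is one of many secondary outcomes in a declared pilot with few expected events. The primary outcomes are set within 8 weeks, inside the described visits, and are unaffected.

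**What to change.** 1. **One clock, with window and capture in agreement, in F1 and G2.** Either restate the outcome as recurrence by 6 months from enrolment and say that record review will capture it, or extend record review to 6 months after each patient's healing date. If an attachment already describes the capture, cite it in both sections.
2. **One named recurrence analysis in G2.** Analyse healed wounds from the healing date, either as time to first recurrence censored at last contact or as a count with a log(weeks at risk) offset. Remove recurrence from the other model list and report the result as descriptive. The time-at-risk term matters most if the window is restated from enrolment, because late healers then have less follow-up.
3. **Optional.** Healed wounds are a subset formed after randomisation. Reporting the proportion healed and recurrence-free at one fixed time among all randomised would keep a randomised comparison. This adds an outcome and is partly a matter of preference.

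**Cost.** Items 1 and 2 need wording in F1 and G2, plus either a shorter recurrence claim or a later record review. For a wound healed at week 16 that review runs to about week 42, which is 16 weeks beyond the cost collection already described. Item 3 also needs status at the fixed time for patients who never healed.
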